For the purpose of this study, analyses will generally be descriptive in nature and will be conducted using SAS statistical software (version 9.3 or higher). Descriptive data regarding patient demographic and clinical characteristics will be calculated. For categorical measures, data will include the frequency (number of cases [n]) and percentage (%) of total study patients observed in each category (N). All variables will be summarised descriptively through tabular displays of mean, median, ranges and standard deviations of continuous variables and frequency distributions of categorical variables. When necessary, continuous

variables also will be categorised into intervals, with the distribution of patients (n, N, %) for each interval provided.

The statistical analysis plan for the study is summarised below. Full details of the statistical analysis will be documented in the statistical and epidemiological analysis plan, which will be finalised before the end of data extraction.

As this is a NIS based on existing data, no formal hypothesis testing or comparisons between treatment cohorts are planned.

i. Main analysis

To account for potential confounding, the study cohorts (patients who received IV rt-PA and patients who did not receive reperfusion treatment) will be 1:1 or 2:1 matched by baseline characteristics using the propensity score matching (PSM) method. Propensity score (PS) will be derived from predicted probabilities of treatment initiation. The PSM aims to balance the 2 treatment cohorts on baseline covariates. The feasibility of PSM will be evaluated based on available sample size and descriptive results. If patient characteristics between the 2 cohorts are significantly different, i.e., less than 50% of patients in the IV rt-PA cohort can be matched to the non-reperfusion cohort based on PSM, the study design will be re-evaluated before proceeding to analysis. The Nearest Neighbour method of PSM will be used to select the matched samples. All the variables listed in the covariates will be considered. Covariates including duration of hospitalization and reasons for untreated with rt-PA are only for descriptive analysis. The distribution of baseline characteristics will be presented before and after the matching process. For baseline covariates that are not sufficiently balanced after PSM, the covariates will be included in an appropriate multivariate model to adjust for those differences.

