7. RESEARCH METHODS

7.1 STUDY DESIGN

This study is a non-interventional study (NIS) based on existing data. We will analyse data of AIS patients aged ≥ 18 years in China collected from the ZSQCC platform. [\[P21-04780\]](#), [\[P21-04783\]](#), [\[P21-04784\]](#), [\[P21-04779\]](#), [\[P21-04782\]](#)

Approximately 11700 AIS patients in total are recorded in the ZSQCC platform and will be analysed in this study. There were approximately 8500 AIS patients (≥ 18 years of age) who were treated with IV rt PA and 3200 patients who were admitted to the hospital within 4.5 hours of symptom onset and did not receive reperfusion treatment from Jan 2017 to Mar 2020. In the China National Stroke Registry I (2007-2008), the 12-month mortality rate for post-stroke patients was approximately 14%. [\[R21-1852\]](#) For this study, it is assumed that 1-year mortality is 12% and 15% for the rt-PA treatment cohort and the cohort who did not receive reperfusion, respectively. In total, 6069 patients with a treatment ratio 2:1 are needed to observe 855 events and to detect the difference (hazard ratio=0.79) with a 2-sided alpha of 0.05 and 90% power. In addition, considering a treatment ratio 1:1 with the same assumption described above with power of 90% at a 2-sided, 5% significant level, roughly 5400 patients are needed to observe 756 events to detect the difference.

[figure not shown]
Patients meeting the inclusion and exclusion criteria will be divided into 2 cohorts:

- IV rt-PA cohort: Patients who received IV rt-PA within 4.5 hours of symptom onset
- Non-reperfusion cohort: Patients who arrived or were admitted to the hospital within 4.5 hours of symptom onset and did not receive any reperfusion treatment

Propensity score matching (PSM) will be used to match the baseline characteristics between the above 2 cohorts. The primary, secondary outcomes, as well as baseline characteristics will be compared between the matched cohorts.

The flow of data selection for each of the 2 reporting patient cohorts is depicted in Figure 1 below.

Figure 1 Patient cohorts selected for the non-interventional study

Note: dotted lines: excluded

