To account for potential confounding, the 2 cohorts will be 1:1 or 2:1 matched by baseline characteristics using the Propensity Score Matching method. The feasibility of PSM will be evaluated based on available sample size and descriptive results. If patient characteristics between the 2 cohorts are significantly different, i.e., less than 50% of patients in the IV rt PA cohort can be matched to the non-reperfusion cohort based on PSM, the study design will be re-evaluated before proceeding to analysis. The PSM aims to balance the 2 cohorts on baseline covariates. The propensity score model will include age, gender, baseline NIHSS/NIHSS categories (0-4, 5-10, 11-15, 16-21, and ≥ 22), pre-stroke mRS, medical insurance status, smoking status, hospital level, diabetes, coronary artery disease, atrial fibrillation, prior stroke/transient ischaemic attack, hypertension, anti-platelet, lipid lowering, oral anticoagulation, and time from symptom onset to hospital admission. The method of Nearest Neighbour matching will be used (a maximum caliper width equal to 0.2 of the standard deviation of the logit of the propensity score) to select the matched samples. Then we will compare the baseline characteristics of the 2 propensity-score-matched cohorts. The absolute standardized difference (ASD) between the 2 PS-matched cohorts will be calculated, where at least 0.1 ASD will be considered a significant difference. For baseline covariates that are not sufficiently balanced after PSM, they will be included in an appropriate multivariate model to adjust for those differences.

For the primary outcome, a comparison of the percentage of 1-year* all-cause mortality (mRS=6) between the 2 matched cohorts will be conducted using a Chi-square test. A Kaplan-Meier curve with log-rank test will be used to analyse the data. Cox regression models will be used to estimate hazard ratios (95% confidence interval) between the 2 matched cohorts.

For the secondary outcomes, descriptive summaries will be conducted in the PS-matched cohorts separately. For the categorical variables including functional independence (mRS 0-2), favourable clinical outcome (mRS 0-1), and mRS 5-6 at 1 year, the Chi-square test and conditional logistic regression model will be conducted. For the distribution of mRS score at 1 year, the Wilcoxon rank sum test and ordinal logistic regression model will be performed to calculate the odds ratio and 95% CI.

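### The matched outcome models adjust only for covariates with an ASD of 0.1 or more, so an imbalance in NIHSS, age or pre-stroke mRS just under that limit stays in the mortality hazard ratio

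*SAP*

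**What the plan says.** SAP 11.1 matches 1:1 or 2:1 by nearest neighbour, with a caliper of 0.2 SD of the logit of the propensity score. Age, baseline NIHSS and pre-stroke mRS are all in the propensity model. Balance is then judged covariate by covariate, "where at least 0.1 ASD will be considered a significant difference". The next sentence is the only adjustment rule: "For baseline covariates that are not sufficiently balanced after PSM, they will be included in an appropriate multivariate model to adjust for those differences". Protocol 9.G.i has the same rule with a 10% limit: "the covariates will be included in an appropriate multivariate model to adjust for those differences".

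The primary model is given as "Cox regression models will be used to estimate hazard ratios (95% confidence interval) between the 2 matched cohorts", with no covariates named. None is named for the conditional logistic or ordinal models either.

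Two steps in this reading are inference. The SAP does not say in so many words that insufficient balance means an ASD of 0.1 or more, and it does not name the multivariate model. The sentence order supports the first. For the second, the Cox, logistic and ordinal models are the only outcome regressions planned.

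**The concern.** The rule treats all covariates alike. An ASD of 0.09 in a weak predictor of death does little. The same ASD in NIHSS or age carries a real difference in expected mortality, yet it triggers no adjustment and the balance table reads as clean.

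The rule can also act one-sidedly. If NIHSS crosses 0.1 and age and pre-stroke mRS sit below it in the opposite prognostic direction, only the NIHSS part is removed and the rest remains.

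Finally, the meaning of the primary HR is settled only after the match is seen. It is marginal if every ASD is below 0.1, and otherwise conditional on a set that the data choose.

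**Working it through.** **1. The planned effect.** SAP 7.1 sizes the study "to detect the difference (hazard ratio=0.79) with a 2-sided alpha of 0.05 and 90% power", and "it is assumed that 1-year mortality is 12% and 15% for the rt-PA treatment cohort and the cohort who did not receive reperfusion". These agree: ln(0.88)/ln(0.85) = 0.787, so 0.79 is a marginal HR. Schoenfeld's formula is events = (1.960 + 1.282)² / [p(1 − p)(ln HR)²], with |ln 0.79| = 0.2357.
- 1:1: 10.51 / (0.25 × 0.0556) = 756, as in "roughly 5400 patients are needed to observe 756 events to detect the difference".
- 2:1: 10.51 / (0.2222 × 0.0556) = 851, close to the 855 in "6069 patients with a treatment ratio 2:1 are needed to observe 855 events".

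The yardstick is therefore 0.2357, and the SE of ln HR at 756 events is 2/√756 = 0.0727.

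**2. Shift from an imbalance that the rule leaves alone.** To first order, shift in ln HR = Σ ASD × ln(HR of death per SD). ASD is set at 0.099. The prognostic HRs are assumptions, because the documents give none.

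| Assumed HR per SD | Shift in ln HR | Share of 0.2357 |
|---|---|---|
| One covariate, 1.2 | 0.018 | 8% |
| One, 1.5 | 0.040 | 17% |
| One, 1.8 | 0.058 | 25% |
| One, 2.0 | 0.069 | 29% |
| One, 2.5 | 0.091 | 38% |
| Three, 1.2 each, same direction | 0.054 | 23% |
| Three, 1.5 each, same direction | 0.120 | 51% |
| Three, 2.0, 1.6 and 1.3, same direction | 0.141 | 60% |

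**3. What one row means.** Take the 1.8 row and 756 events; 0.058/0.0727 = 0.80. With no true effect, the chance that a two-sided 5% test rejects is 1 − Φ(1.96 − 0.80) + Φ(−1.96 − 0.80), about 13%. If the shift runs toward the null, power at 0.79 is Φ[(0.2357 − 0.0582)/0.0727 − 1.96], about 68%. The estimated HR would centre on about 0.745 or 0.84 instead of 0.79, depending on direction.

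**4. Check of the approximation.** Cox models were fitted to 400,000 simulated patients, with 13% to 15% deaths and covariate correlation 0.2. The shifts were 23% to 24% of the planned effect for one covariate at 1.8, 48% to 50% for three at 1.5, and 53% to 56% for 2.0, 1.6 and 1.3. In the 1.8 case with no treatment effect, the unadjusted HR was 1.018 under balance and 0.961 under imbalance. With the covariate in the model under imbalance it was again 1.018. The excess over 1.00 is simulation error common to the runs. Adjustment removes the shift.

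**5. When such an imbalance would occur.** By chance alone it is unlikely: at 2,700 per arm the SE of a standardised difference is √(2/2700) = 0.027, so 0.099 is about 3.6 SEs. Greedy matching can, however, leave a systematic difference, because about 8,500 treated patients compete for about 3,200 controls (SAP 7.1). In simulations of 11,700 patients with a 0.2 SD caliper and assumed propensity coefficients:
- Random orders, and matching from the control side, left mean ASDs of 0.006 to 0.014 for NIHSS and at most 0.017 for age and pre-stroke mRS. Bias with random order was negligible.
- Taking treated patients first, in descending propensity score, left ASDs of about 0.04 to 0.20. The unadjusted ln HR shifted by about 0.07 to 0.18, and adjusting for all three covariates largely removed the shift.

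SAP 10.1 and 11.1 name the package, the method and the caliper, but no order.

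**6. Opposing imbalances.** One descending-order scenario assumed that treated patients have higher NIHSS, are younger and have lower pre-stroke mRS. The assumed log hazards were 0.8 per SD of NIHSS, 0.55 per SD of age and 0.2 per mRS point (about 3,190 pairs, 150 runs). Standardised differences after matching were +0.14 for NIHSS and −0.07 for each of the others, so the rule adjusts for NIHSS only. With no true effect:
- Unadjusted: ln HR +0.054, type I error 13%.
- NIHSS only, as the rule directs: −0.068, 16%, in favour of rt-PA.
- All three: 0.000, 3%.

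Monte Carlo error on these rates is about 1 to 3 percentage points.

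**The case against.** The plan does control these covariates. They are in the propensity model, a caliper applies, balance is checked, and any remaining imbalance at or above the limit is adjusted for. Always adjusting for prognostic factors is a second layer, and its absence is not an error in itself. An ASD of 0.099 is a near-worst case, and under random order the problem vanishes. One could also say that the direct remedy is to state the matching order. All of this stands, and it is why the point is a conditional risk. It does not settle the matter, because the order is open and the limit takes no account of prognosis. That opposing imbalances may cancel is only partly reassuring, since the rule can remove one side and leave the other.

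A reader might go further in three ways that the documents do not support:
- That the shift is about a quarter of the planned effect. This holds only for particular assumed strengths, such as one covariate at 1.8 per SD; the range is wide.
- That the unadjusted HR is wrong because omitting strong predictors pulls it toward 1. That is non-collapsibility. The planned 0.79 is itself marginal, so the unadjusted matched HR is a legitimate target when balance is good.
- That the odds ratios for mRS shift by similar amounts. The same omission applies to those models, but no odds-ratio shift has been calculated.

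**Conclusion.** The point holds as a conditional risk that is cheap to remove. As written, the adjustment rule lets an imbalance below 0.1 in a strong predictor of death pass into the primary HR. It can also correct one imbalance while leaving an opposing one. At an ASD of 0.099 the shift is about 8% to 38% of |ln 0.79| for one covariate, and up to about 60% if all three are imbalanced in the same direction. The simulated maximum was slightly lower, at 53% to 56%. These figures rest on assumed prognostic HRs and on imbalances near the limit. Such imbalances are mainly to be expected if treated patients are matched in descending propensity-score order, and hardly at all with random order. Separately from size, whether the primary HR is marginal or conditional is not fixed before the match is seen.

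**What to change.** In SAP 11.1, replace the ASD-triggered rule with wording such as:

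> The Cox model for the primary outcome and the logistic and ordinal models for the mRS outcomes, fitted in the matched set, include treatment, age, baseline NIHSS and pre-stroke mRS in all cases. The unadjusted matched HR is reported alongside as the marginal estimate corresponding to the planned HR of 0.79. Other covariates with an ASD of 0.1 or more after matching are added only in a sensitivity analysis.

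The form in which NIHSS enters should be stated too, since SAP 11.1 leaves open whether it is continuous or in five categories. The change should be recorded as a departure from Protocol 9.G.i. Stating the matching order in the same section would show whether the risk applies, but would not by itself fix the primary model.

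The cost is a few SAP sentences and three model terms already in the propensity model. Age and NIHSS are complete in every included patient, because missing either is an exclusion. There are two downsides. The adjusted HR is conditional and slightly further from 1 than the marginal HR, which is why both should be shown. Missing pre-stroke mRS values are median-imputed (SAP 10.2), so adjustment for that covariate is less complete than the simulations assume.

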All the data cleaning, integration, analysis will be conducted under the guidance and supervision of ZSQCC.

Greater details are documented in the NIS-DMRP.

I) LIMITATIONS OF THE RESEARCH METHODS

This is a NIS based on existing data, although PSM is used, we cannot rule out the influence of other unmeasured confounding factors. In this study, potential limitations of the study design can be listed as:

- Zhejiang is an economically advanced province in China. In this study, AIS patients who received treatment or arrived or were admitted to the hospital within 4.5 hours of symptom onset in this study will be analysed and may not be fully representative to all AIS patients in China.
- AIS patient data from the ZSQCC platform were reported by the stroke centres without external monitoring.

- The treatment adapted for AIS patients may be different among stroke centres.
- The completeness of the captured data and potential for misclassification of data could differ among stroke centres.
- Some important variables may not be collected in the database. For example, patients' education level was not available in the database.

J) OTHER ASPECTS**i. Data quality assurance**

A quality assurance audit/inspection of this study may be conducted by the investigator or by IRBs / Independent Ethics Committee (IECs) or by regulatory authorities. The quality assurance auditor will have access to the investigator's study-related files and correspondence of this study.

ii. Study records**1. Source documents**

Source documents provide evidence for the existence of the patient and substantiate the integrity of the data extracted.

2. Direct access to source data and documents

The investigator/institution will permit study-related audits, IRB/IEC review and regulatory inspection, providing direct access to all related database/documents. All source documents, including progress notes must be available at all times for review by the inspection by health authorities.

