7.2 SETTING

In this study, AIS patient data from 80 stroke centres in the ZSQCC platform from January 2017 to March 2020 will be used.

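### The planned analyses make no allowance for the 80 centres, so the primary hazard ratio interval tends to be too narrow if rt-PA use and mortality both vary by centre

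*SAP*

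**What the plan says.** SAP 7.2 sets the scope: "AIS patient data from 80 stroke centres in the ZSQCC platform from January 2017 to March 2020 will be used".

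For 1-year mortality, SAP 11.1 plans three things. A comparison of percentages "between the 2 matched cohorts will be conducted using a Chi-square test". Then: "A Kaplan-Meier curve with log-rank test will be used to analyse the data". Then: "Cox regression models will be used to estimate hazard ratios (95% confidence interval) between the 2 matched cohorts". The three binary mRS outcomes get a chi-square test and conditional logistic regression; the mRS distribution gets a Wilcoxon rank sum test and ordinal logistic regression. No variance estimator is named for any of them, and centre appears in none.

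Matching is nearest-neighbour with a caliper on the propensity score. The pairs or sets need not come from one centre. Among the score's covariates, the only one describing the centre is hospital level (Grade 2 or 3).

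The limitations in Protocol section 9 (I) acknowledge that "The treatment adapted for AIS patients may be different among stroke centres", and that data completeness and misclassification could also differ. No analysis step follows from this in either document.

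**The concern.** Patients treated in one hospital share its stroke care, case mix and recording habits, so their mortality may be correlated. If every centre treated the same share of its patients with rt-PA, a centre's effect on mortality would fall on both cohorts alike and cancel. If some centres give rt-PA much more often than others, the two cohorts draw on the centres in different proportions, and the centre effects add variation to the log hazard ratio that a model assuming independent patients does not count.

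The 95% interval for the primary hazard ratio would then claim more precision than the data hold, and the chi-square and log-rank tests would reject too often at a nominal two-sided 5%. This concerns the error bars. It is separate from which covariates enter the propensity score and from dependence within matched sets.

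**Working it through.** **Does the sample size hide an allowance for clustering?** SAP 7.1 says "it is assumed that 1-year mortality is 12% and 15% for the rt-PA treatment cohort and the cohort who did not receive reperfusion". At 2:1, "6069 patients with a treatment ratio 2:1 are needed to observe 855 events and to detect the difference (hazard ratio=0.79"; at 1:1, "roughly 5400 patients are needed to observe 756 events to detect the difference". Alpha is two-sided 0.05 and power is 90%.

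- Hazard ratio: ln(0.88)/ln(0.85) = 0.787, stated as 0.79.
- Events by Schoenfeld's formula, (1.960 + 1.282)² / [p(1−p)(ln 0.79)²], where p is the rt-PA share: 757 at 1:1 (stated 756) and 851 at 2:1 (stated 855).
- Patients, from comparing 15% with 12%: 5450 at 1:1 (stated about 5400) and 6090 at 2:1 (stated 6069).

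All agree within 3%. These formulas assume independent patients, so no design effect is built in.

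**Design effect.** For a treatment that varies within centres, approximately

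DE = 1 + (m − 1) × ICC(mortality) × ICC(rt-PA use),

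and the correct standard error is √DE times the model one. Patients per centre: m = 5400/80 = 67.5 at 1:1 and 6069/80 = 75.9 at 2:1. The documents give neither ICC, so both are assumptions.

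| Case (equal centres) | DE | SE ratio |
|---|---|---|
| 1:1, ICCs 0.005 and 0.1 | 1 + 66.5 × 0.0005 = 1.03 | 1.02 |
| 1:1, ICCs 0.02 and 0.1 (mid case) | 1 + 66.5 × 0.002 = 1.13 | 1.06 |
| 2:1, ICCs 0.02 and 0.3 | 1 + 74.9 × 0.006 = 1.45 | 1.20 |
| Either ratio, no variation in rt-PA use | 1 | 1.00 |

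**Mid case in full (1:1).**
- Model SE of the log hazard ratio: √(4/756) = 0.0727. Around 0.79 the interval is 0.685 to 0.911.
- Corrected SE: 0.0727 × 1.064 = 0.0774. The interval becomes 0.679 to 0.919, which is 6% wider on the log scale.
- Actual alpha of the uncorrected test: 2 × [1 − Φ(1.96/1.064)] = 0.066.
- Power with the correct SE: 756/1.133 = 667 effective events, giving 86% instead of 90%.

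**What would make it larger.**
- Unequal centres: with a coefficient of variation of centre size of 1, m is replaced by 2m. The mid-case DE becomes 1.27 at 1:1 and 1.30 at 2:1.
- Larger ICCs: at 1:1, 0.05 and 0.30 give DE 2.00, an interval 1.41 times as wide.
- More patients: if all 3200 non-reperfusion patients were matched 2:1, m = 9600/80 = 120, and ICCs of 0.02 and 0.3 give an SE ratio of 1.31.

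**Simulation check.** 80 centres, 5400 patients, true hazard ratio 1, 4000 runs per setting, log hazard ratio estimated from 1-year mortality by the complementary log-log. The ranges cover equal and unequal centre sizes.

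| SD between centres: log hazard / logit of rt-PA use | True SE ÷ model SE | Actual alpha |
|---|---|---|
| No variation in rt-PA use | 0.97 to 1.02 | 0.04 to 0.05 |
| Moderate: 0.3 / 0.5 to 1.0 | 1.02 to 1.14 | 0.058 to 0.084 |
| Strong: 0.5 / 1.0 | 1.16 to 1.30 | 0.09 to 0.14 |

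Mortality and rt-PA use must both vary by centre for the model SE to be materially too small.

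**The case against.** **The harm is conditional.** The protocol says only that treatment may differ by centre. It does not say that mortality does, and it gives no ICC. Hospital level in the propensity score removes the part of centre variation that grade explains. This stands, and it is why the size can only be given as a range.

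**Conditional logistic regression already allows for dependence.** It does so within its strata, presumably the matched sets. Matched sets are not centres, so two patients of one hospital in different sets still count as independent. It would be wrong to say that every planned analysis ignores all dependence, but none allows for centre.

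**The net direction is uncertain.** Ignoring the matched sets in the Cox model can make its interval somewhat too wide, which would offset part of the effect. This stands. It does not justify leaving centre out.

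**No testing is planned.** Protocol section 9 (G) disclaims formal hypothesis testing and comparison between the cohorts. The SAP nevertheless specifies chi-square and log-rank tests, and the interval is reported either way.

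**Clustered standard errors do not remove confounding by centre.** This is correct. With a correlation of −0.3 between a centre's rt-PA use and its mortality, the simulated mean log hazard ratio moved by −0.04 to −0.07 under a true hazard ratio of 1. A robust variance leaves that shift in place.

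**Conclusion.** The omission is real, and its effect on the primary interval is conditional. If rt-PA use and mortality both vary by centre beyond hospital level, the model-based interval omits that dependence and tends to be too narrow. At the planned size, with equal centres and the assumed ICCs of 0.005 to 0.02 and 0.1 to 0.3, the understatement of the standard error is modest: a factor of 1.02 to 1.20, with a mid case of 1.06.

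A reader might infer that the interval is certainly too narrow, or that the false-positive rate is two or more times nominal. The documents support neither. They contain no measure of between-centre variation in mortality or rt-PA use, and in simulation rates of about 0.10 or more in the absence of confounding by centre needed strong variation in both. Nor do they support the opposite reading that centre can safely be ignored, since the protocol itself lists differences among centres as a limitation.

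**What to change.** In SAP 11.1:

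1. Report the primary Cox hazard ratio with a sandwich variance clustered on centre; 80 clusters are enough for this to be usable. Base the primary inference on it and not on the unclustered chi-square or log-rank test.
2. Use centre-clustered variance for the mortality percentages and the ordinal model.
3. For the three binary mRS outcomes, fit a marginal logistic model (GEE) clustered on centre in place of, or alongside, conditional logistic regression.
4. Add a Cox model stratified by centre as a sensitivity analysis, since step 1 leaves confounding by centre untouched.

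The cost is slightly wider intervals and some extra programming. The change is small for the Cox model and larger for the binary outcomes, where a different procedure is needed. The reporting-centre identifier must also be carried into the analysis dataset: SAP 8.3 lists hospital level but not centre, although SAP section 9 says the characteristics of each centre are recorded. If between-centre variation proves negligible, little precision is lost.
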